11. SAFETY REPORTING

Safety reporting for each participant will begin from the first point of administration of the intervention (tooth brushing) and will end when the participant has reached their final main follow up time point, at 90 days. This is a low risk, pragmatic study where the trial interventions is basic personal hygiene for patients. In light of this, we do not anticipate many serious adverse events (SAEs) associated with the study intervention.

The study team does not endorse or recommend the use of pink foam swabs during the study and this information will be made clear during the training for staff. The pink foam end can be bitten off and cause choking. As a result pink foam swabs are banned in Wales, and not used in Mouth Care Matters toolkits.

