6.3.2 Discharged patients and transfers to other healthcare settings

When patients are discharged they will be given their oral health pack to take with them to continue undertaking oral care after discharge, up to a maximum of 4 weeks. They or their carers will be advised to switch to using fluoride toothpaste at this point. If patients are transferred to other wards for continuing therapy, these packs will be transferred along with the patients, but continuing daily data collection will not be undertaken in those wards. These patients will also be advised to continue undertaking mouth care up to a maximum of 4 weeks and thereafter advised to use fluoride toothpaste. We will explore the feasibility of collecting hospital record data as well as follow-up PROMs.

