8.2 Mouth care intervention

In participating units, for each recruited patient we will ask nursing staff to complete an oral health assessment tool once just after recruitment. We will provide laminated posters which can be displayed above the participant's bed.

Each recruited participant will be given a mouth care pack at recruitment, consisting of a bag containing a bottle of alcohol free Chlorhexidine 0.2% , a 10ml tube of lip moisturiser and a small headed soft toothbrush, contained within a bag branded with the study logo. We will ask staff to store the bag on the bedside cabinet as a reminder. This pack can be taken with the patient on discharge or at transfer to other care settings.

After recruitment participants will be offered mouth care three times daily and we will ask staff to document each of these episodes on a simple daily recording sheet, provided as part of the study. Participants will be encouraged to take part in as much of their mouth care as possible, and staff will be trained in dementia-friendly techniques (e.g. hand over hand techniques) using the training videos described above. Healthcare assistants will assist the patient where necessary (ranging from verbal prompting to physical assistance) to undertake the mouth care intervention (see Table 2) three times per day, before/after meals. Patients with delirium and dementia may be shown a short video on iPad explaining what will happen. If the intervention is declined, a more limited intervention will be offered (e.g. lip moisturiser only), and the intervention will be offered again at the next round.

Mouth care will be recorded on a daily recording sheet either by staff or patient, documenting whether the intervention was delivered, any issues, and how much help was needed.

Table 2: Mouth care intervention

Dentition	Action
Teeth	
 • Put on the appropriate PPE • Provide the mouth care kit • Dip soft toothbrush in chlorhexidine mouthwash, squeeze once • Brush teeth, gums and tongue, 2 minutes using clock in bay • Apply lip moisturiser

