	Oxygen level/sats on day starting abx			
Other outcome data	Length of stay- acute hospital Death in hospital Death within 30 days EQ-5D at 90 days	Hospital records, contact with participant or consultee	All recruited participants	Once
Discharges/transfers	Discharge Transfer destination Discharge date	Hospital records, contact with participant or consultee	All recruited participants	Once

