12.1 Statistical Analysis

12.1.1 Quantitative data analysis

We will measure and review the primary outcome monthly at each unit. Secondary outcomes relating to recruitment and mouth care episodes will also be collected and reviewed monthly. These will be analysed using simple descriptive statistical techniques, and may be displayed using control charts. Antibiotic use (data collected will include: antibiotic name, dose, frequency and length of course) will be presented with summary statistics. We will compare rates of antibiotic prescribing across trial wards to determine baseline variation and determine timing of antibiotic prescriptions using first day antibiotic prescribed.

For participants moved to community hospitals in Trusts where there is no electronic prescribing, a research nurse will phone the community hospital weekly to check for any prescribed antibiotics. Intra-cluster correlation estimates of outcomes derived from this trial will be compared with those from the SOCLE II trial (26) and used to inform the sample size estimation for a larger trial.

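### Safety reporting is declared to 90 days, but no active or scheduled safety ascertainment is specified after the ward, and the 90 days has two different starting points

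*Protocol*

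**What the plan says.** - **Safety window.** Section 11 starts safety reporting at the first tooth brushing and says it "will end when the participant has reached their final main follow up time point, at 90 days".
- **Use after the ward.** Under Section 6.3.2, discharged participants take the pack with them "to continue undertaking oral care after discharge, up to a maximum of 4 weeks". Section 8.2 says the pack contains "a bottle of alcohol free Chlorhexidine 0.2" per cent. Participants transferred elsewhere take it too, but "continuing daily data collection will not be undertaken in those wards". Of later data, Section 6.3.2 says only: "We will explore the feasibility of collecting hospital record data as well as follow-up PROMs".
- **How events enter.** Sections 11.2 and 11.3 start the reporting clock when the local team or investigator learns of an event. Only related events are collected.
- **What is collected later.** Table 3 (Section 10.1.2) lists in-hospital death, "Death within 30 days" and EQ-5D at 90 days. Its antibiotic and HAP rows apply only while the participant is on the ward. For Trusts without electronic prescribing, Section 12.1.1 adds that "a research nurse will phone the community hospital weekly to check for any prescribed antibiotics".
- **Origin of the 90 days.** Section 10.1.2 counts the EQ-5D-5L contact from discharge. Section 12.2 counts it from admission. Section 11 names no origin.

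**The concern.** A stated window implies that events within it are looked for. Several events named in Section 11.3 could happen during unsupervised use: swallowing or aspirating mouthwash, staining, minor mouth injury, slips on spilled mouthwash. Section 12.3 assumes that 40% of patients need a consultee, and such patients are poorly placed to volunteer a report. Related and unexpected SAEs have to reach the REC (Section 11.2). There is no separate safety committee, so the oversight committee's safety review (Section 14.5) depends on the same data. A report of few or no related events to 90 days might then mean only that nobody asked, and it would inform the larger trial.

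Death status raises a second issue. Section 12.2 compares EQ-5D-5L between participants with HAP and matched controls, and aims to take account of mortality. Section 3 cites HAP mortality of up to 29%. If deaths outside hospital after day 30 are not recorded, an absent 90-day questionnaire may mean death or non-response, possibly in different proportions in the two groups. That would also blur the planned exploration of missing economic data.

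**Working it through.** The protocol gives no figure to reproduce here. The check sets the passages side by side and then counts days.

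**Step 1: which post-ward channel carries a safety question?**

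| Channel | Section | What it is stated to collect |
|---|---|---|
| Daily mouth care sheet | 6.3.1, 6.3.2 | Stops on leaving the ward |
| Antibiotic and HAP rows | Table 3 | Ward stay only |
| Weekly call to some community hospitals | 12.1.1 | Antibiotics |
| Contact by phone, paper or email, proxy allowed | 10.1.2, 12.2 | EQ-5D-5L |
| Hospital records, or contact with participant or consultee | Table 3 | Stay, death in hospital, death to 30 days, EQ-5D, discharge details |
| Hospital data and follow-up for those moved with COVID-19, with consent | 6.3.1 | Content not specified |
| AE and SAE forms | 11.2, 11.3 | Related events, once someone has told the team |

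Only the last row concerns safety, and it depends on a report arriving. No scheduled question, readmission check or safety contact after the ward is described.

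**Step 2: how much of the window lies after the ward?** Let L be the ward stay in days. Section 4.2 gives an average above 7 days; the range 4 to 28 is my assumption.

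- Counted from admission: post-ward days = 90 − L. For L = 7, 90 − 7 = 83 (83/90 = 92%). For L = 4, 86; for L = 28, 62.
- Counted from discharge: post-ward days = 90 whatever L is, and the window ends on day L + 90 from admission. For L = 7 that is day 97; for L = 4, day 94; for L = 28, day 118.

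Reporting starts at first brushing rather than at admission, so the ward share is if anything smaller than this.

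**Step 3: how much product use lies after the ward?** If the 4 weeks run from discharge, up to 28 days. If they mean total use starting at admission, up to 28 − L, which is 28 − 7 = 21 days for a 7-day stay. On either reading, post-ward use is allowed without daily recording.

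**Step 4: death status.** Days 31 to 90 are 60 of 90 days (67%) if the 30-day and 90-day clocks share an origin, which the protocol does not state. In that stretch, death outside hospital is not a listed item, while EQ-5D is due at its end.

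**The case against.** The strongest reply is that passive, related-only reporting is a deliberate and explained choice for a low-risk hygiene intervention, with safety review by an oversight committee. The AE and SAE forms, the SAE guidance in the site file and the patient questionnaires are not reproduced in the protocol. Table 3 has no adverse-event row even for the ward, so its silence about later safety data is weak evidence. All of this stands, and it limits the claim to what the protocol specifies. It does not remove the gap: a related event at home still has to reach the team, and Sections 10 and 11, where contacts are laid out, provide no route that asks.

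Four stronger readings are tempting, and the protocol does not support them.

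- A reader might infer that there is no means of ascertainment at all. Awareness-based reporting covers the whole window, and the contacts in the table above exist.
- A reader might infer that death recording ends at day 30. In-hospital death carries no time limit in Table 3; only deaths outside hospital are unlisted after that day.
- A reader might infer that permitted use outlasts the 30-day death item, from 7 + 28 = 35 days. The origin of the 30 days is not stated, and counted from discharge it would cover the 28 days of use. The 4 weeks may also mean total use.
- A reader might infer that participants who die are counted as having missing economic data, and put a number on it. The protocol neither defines complete data for that outcome nor gives mortality for the interval. The rule may sit in the SAP or a health-economics plan. The 90-day contact, or a records check, may also reveal a death.

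**Conclusion.** The point holds in a limited form. Safety reporting is declared to 90 days and the chlorhexidine pack may be used after the ward, but no active or scheduled safety ascertainment is specified there. For a 7-day stay, 83 of 90 days (from admission) or 90 of 97 (from discharge) rest on volunteered reports. The protocol allows the direction of the error to be stated (under-counting of related events), but not its size.

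Out-of-hospital death between day 30 and the 90-day EQ-5D point is not a listed item, so a participant who has died may not be distinguishable from a non-responder. The end of the safety window is itself unclear, because the 90-day contact has two origins that differ by the length of stay.

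The day counts rest on the 7-day stay, which is the lower bound of the stated ward average, and on the assumed 4-to-28-day range. The conclusion also rests on the forms not shown containing no scheduled safety question.

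**What to change.** 1. State one origin for the 90 days, and reconcile Sections 10.1.2, 11 and 12.2 with it.
2. Add a short, fixed question set on the related adverse events named in Section 11.3 to the 90-day contact already planned for EQ-5D-5L, in a form that works by phone, paper, email and proxy. Add it also to the existing weekly community-hospital call. That call covers only Trusts without electronic prescribing, so the 90-day contact has to carry the question for everyone else.
3. In Table 3, replace the 30-day death item with date of death up to the 90-day point, taken from hospital records or contact and checked before the EQ-5D-5L contact is made. Thirty-day death can still be derived once its origin is stated.

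If these are not adopted, Section 11 should say that safety reporting after the ward is passive, and the study report should not present the result as actively ascertained 90-day safety.

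The cost is amendment wording, a few questions on existing contacts and one date field. The drawbacks are slightly longer contacts, recall error in a question asked at 90 days about earlier use, and higher reported counts of adverse events and deaths. No change to the intervention or its duration is proposed.

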11.1 Definition of Serious Adverse Events (SAE)

A serious adverse event is any untoward medical occurrence that:

- results in death
- is life-threatening
- requires inpatient hospitalisation or prolongation of existing hospitalisation
- results in persistent or significant disability/incapacity
- consists of a congenital anomaly or birth defect

Other 'important medical events' may also be considered a serious adverse event when, based upon appropriate medical judgement, the event may jeopardise the participant and may require medical or surgical intervention to prevent one of the outcomes listed above.

NOTE: The term "life-threatening" in the definition of "serious" refers to an event in which the participant was at risk of death at the time of the event; it does not refer to an event which hypothetically might have caused death if it were more severe.

11.2 Reporting procedures for SAEs

A SAE occurring to a participant should be reported to the REC that gave a favourable opinion of the study where in the opinion of the Chief Investigator (CI) the event was 'related' (resulted from administration of any of the research procedures) and 'unexpected' in relation to those procedures. Reports of related and unexpected SAEs should be submitted within 15 working days of the Chief Investigator becoming aware of the event, using the HRA report of serious adverse event form (see HRA website). As the study treatment procedures investigated forms part of basic personal hygiene for participants, we will not be collecting unrelated SAEs.

When the local research team becomes aware of an SAE in a trial participant, the PI will review the SAE locally and make a decision about the causality (i.e. likelihood of the event to be related/attributed to the intervention). Further details on grades of causality can be found in the SAE reporting guidelines document available in the ISF. Following the assessment of causality the PI will assess any related events for expectedness. For any SAEs assessed as unexpected and potentially

related, the details of the event will be entered on an SAE reporting form on the database, and the local research team will notify the central trial team via email or telephone within 24 hours of the PI becoming aware of the event. Once the SAE form is received, causality and expectedness will be confirmed by the CI or delegate (Nominated Person). In the event that consensus is not reached between the PI and Nominated Person about assessment of causality and expectedness, this will be escalated to the CI for further discussion. However, if no consensus decision is reached about expectedness after further discussion within one working day, and the SAE is judged to be unexpected by any one of either the Principal Investigator (PI), Nominated Person or CI, the event will be classified as an unexpected event.

11.3 Foreseeable AEs & SAEs

All related AEs should be reported using the study AE reporting forms within 48 hours of the Investigator becoming aware of the event. As the study treatment procedures investigated forms part of basic personal hygiene for participants, we will not be collecting unrelated AEs or SAEs. An SAE form may be triggered following the initial AE form as applicable. This is a low risk study, and potential related adverse events would include:

Expected AEs include:

- Confrontational behaviour around mouth care and towards staff (participants with Dementia)
- Staining on teeth as a result of Chlorhexidine use (e.g. consuming tea straight after intervention)
- Gum bleeding
- Minor accidental injury to mouth while brushing
- Tooth loss
- Broken dentures or loss of dentures
- Spillage of mouthwash resulting in slips and falls
- COVID infection risk to staff and patients as similar to all inpatients

Unexpected AEs include:

- Aspiration of mouthwash
- Drinking mouthwash
- Allergic reaction to lip moisturiser

Training in delivering oral interventions to patients with delirium/dementia will be delivered by our speech and language team, who have a wealth of experience in this area. Confrontational behaviour is common in this population and the ward teams are generally experienced in dealing with patients with delirium or dementia, as it forms a part of 'normal business'. Not opening the mouth will be taken as lack of consent to proceed with the intervention.

Mouth care is not classed as an aerosol generating procedure and standard ward PPE, as per each sites individual hospital guidelines, will be worn. This could include, gloves, plastic apron, fluid repellent surgical face mask and visor (see, Section 14.1).

SAEs/AEs that are foreseeable, or expected, in the treatment of hip fractures/medical procedures do not need to be reported and only variables on the CRF and/or Patient Questionnaires will be collected including HAP episodes.

12. STATISTICS AND DATA ANALYSIS

Permission will be obtained to transfer anonymised data to York Trials Unit for analysis. A pre-specified Statistical Analysis Plan (SAP) will be developed and signed off prior to database lock and commencement of the analysis.

12.1 Statistical Analysis

12.1.1 Quantitative data analysis

We will measure and review the primary outcome monthly at each unit. Secondary outcomes relating to recruitment and mouth care episodes will also be collected and reviewed monthly. These will be analysed using simple descriptive statistical techniques, and may be displayed using control charts. Antibiotic use (data collected will include: antibiotic name, dose, frequency and length of course) will be presented with summary statistics. We will compare rates of antibiotic prescribing across trial wards to determine baseline variation and determine timing of antibiotic prescriptions using first day antibiotic prescribed.

For participants moved to community hospitals in Trusts where there is no electronic prescribing, a research nurse will phone the community hospital weekly to check for any prescribed antibiotics. Intra-cluster correlation estimates of outcomes derived from this trial will be compared with those from the SOCLE II trial (26) and used to inform the sample size estimation for a larger trial.

12.1.2 Qualitative data analysis

The formal data for analysis will consist of anonymised transcripts, field notes of observation and reflective notes made by researchers. The constant comparative method of analysis will be used with an iterative process of data collection and analysis. A coding frame will be developed by the qualitative team at York Trials Unit, informed by the core concepts of NPT and the data will be coded by the researchers. A software package (QSR NVivo 11) will be used to facilitate data management.

12.2 Economic analysis

The feasibility of undertaking an economic evaluation of the previously described mouth care intervention versus usual care will be explored in order to inform a future trial. The economic analysis aims to incorporate the impact of the intervention in terms of potential HAP prevention and the associated costs and outcomes of HAP, i.e. extended length of stay, antibiotic use, and impact on health-related quality of life and mortality. The health economics component of the feasibility study will include consideration of an appropriate evaluation framework, the appropriate instruments, and data collection methods for the cost and outcome data used for the economic analysis. As part of this, the feasibility of collecting economic data via medical records/databases, such as the NHFD and PROMs, will be assessed. An indication of costs associated with the intervention will be provided.

The feasibility of collecting health-related quality of life (HRQoL) data via the EQ-5D-5L (27) will be investigated. EQ-5D-5L data will be collected from all patients, and patients will be asked to describe their health before admission, at admission and 90 days after admission by phone, paper or email; for patients with hip fracture this will be the day before their hip fracture (NHFD 2018). EQ-5D-5L questionnaires will be compared between a subset of patients who developed HAP, and from age-sex matched controls who did not develop HAP. The EQ-5D-5L will be completed by a proxy where the patient is unable to complete the questionnaire themselves. The HRQoL for patients who develop HAP will thereby be compared to the HRQoL for patients who did not develop HAP, in order to estimate the utility decrement associated with HAP.

An NHS costing perspective will be taken for the analysis, with a focus on health care utilisation within secondary care; specifically length of hospital stay for patients who developed HAP versus those who did not develop HAP, obtained via the various hospital databases, including NHFD for participants recruited who have sustain a hip fracture The cost of antibiotics for HAP will also be estimated. Unit costs feeding into the analysis will be derived from established costing sources, such as NHS Reference Costs (28) and the British National Formulary (29).

In order to accurately capture the patient pathway in terms of health care resource use, the patterns of care for patients will be described at hospital level (primary care resource use is unlikely to be significant for this patient group as HAP mainly occurs while still hospitalised). This will help to determine whether additional resource utilisation within primary care would need to be collected for a potential future trial. The cost of the intervention will be estimated, including staff time to deliver the intervention, training costs and costs of the mouth wash etc. versus the cost of usual mouth care.

To inform missing data methods and improve completion rates for a full trial, the missing economic data will be explored as part of this feasibility study. A full economic evaluation will not be undertaken, due to looking at the feasibility here rather than conducting a full trial. However, findings regarding the health economic component of this study will be used to make refinements and improvements to the methods used for a health economic analysis of a future trial, which would involve a full economic evaluation being conducted.

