1. STUDY SUMMARY

Study Title	Mouth cAre to Prevent Pneumonia in older people Study (MAPPS): a feasibility study
Short Study Title	Mouth cAre to Prevent Pneumonia in older people Study (MAPPS)
Study Rationale	
Hospital-acquired pneumonia (HAP) is the commonest healthcare associated infection in Europe. Up to 70% of patients with HAP may die, and there are currently no prevention strategies being used in hospitals to mitigate this. HAP is costly, to hospitals because of excess length of stay of 10-12 days, and to patients because of the time spent being ill, physical deconditioning, loss of independence and death. HAP is common, and occurs because certain bacteria appear in the mouth when patients become unwell, and these may travel from the mouth to the lungs via a process called aspiration. Frequent mouth care might prevent HAP by reducing the number of these organisms. The evidence is not yet strong enough to make changes to clinical care, and a large trial is needed to test the hypothesis. However some initial work is required to guide the successful design and delivery of a larger, definitive trial.
 
This study will undertake that initial work, focussing on the recruitment of the high risk population (patients with delirium and dementia) and delivery of the intervention to this hard to reach group. We will make the information learned from this work easily available for other researchers internationally, in order to improve the delivery of similar trials elsewhere.

Population	Units/wards which admits patients with Hip fracture; Medical patients within these wards will also be included
Intervention	
Patient: Three times daily tooth brushing with an antiseptic mouthwash (Chlorhexidine 0.2%) and application of lip moisturiser.
 
Staff: Mouth care education, training, documentation and process intervention delivered as part of the study

Study Design	MAPPS is a multi-centre mixed methods feasibility study, which utilises a stepped-wedge, cluster randomised design. The study will test the feasibility of delivering a mouth care intervention designed to prevent HAP in a real world ward based setting, including a subset of participant and staff qualitative interviews.
Study Duration	18 months.
Study Centre(s)	Four wards which admit patients with hip fracture and medical patients will be the clusters.
Objectives	We aim to understand how to deliver consistently a mouth care intervention to older patients in a ward setting.

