2. FEASIBILITY SCHEDULE

Table 1: Project timeline

	0	1-3	4-6	7-9	10-12	13-15	16-18
Site 1		(150) 56	(150) 112	(150) 112	(150) 112	(150) 112	
Site 2			(150) 56	(150) 112	(150) 112	(150) 112	
Site 3				(150) 56	(150) 112	(150) 112	
Site 4					(120) 45	(120) 90	
Video		Filming					
Interviews		Focus groups					
HAP data							
Health Ec data							
Analysis							

(Total eligible) estimate recruited, based on 75% recruitment after training/transition period

Monthly data collection of mouth care delivered on single day, per unit pre-intervention

Training and transition to intervention

Intervention

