3. BACKGROUND

Hospital acquired pneumonia (HAP) is the commonest healthcare acquired infection, and accounts for 26% of all healthcare associated infections in Europe (1). It is a leading cause of death in hospitalised patients, with a mortality of up to 29% (2). Broad-spectrum antibiotics, used to treat HAP, contribute to the threat of antimicrobial resistance, and consequently have implications for safe healthcare in the near future (3). Patients stay in hospital an average additional 12 days because of HAP (4, 5), and a single day in hospital is estimated to cost £333 locally.

Approximately 1.5% of all hospital in-patients develop HAP (6); on a national scale, the potential individual, economic and system gains from reducing HAP are substantial. The incidence of other healthcare associated infections has been reduced by care units (7). A significant evidence base exists around prevention of ventilator associated pneumonia (8), but two-thirds of patients who develop HAP have never been ventilated (7), and HAP remains an under researched condition.

When people become unwell, particular bacteria (typically Enterobacteriaceae, Staphylococcus aureus and Pseudomonas aeruginosa) become dominant within the microbiome at multiple body sites and pose the risk of secondary infection (9). HAP occurs predominantly due to aspiration of these organisms from the mouth to the lungs (10). Patients are six times more likely to develop HAP if the mouth is persistently colonised by one of these bacteria (11). These bacteria are not usually native to the healthy mouth (12).

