Admission rates per month are expected to be approximately 50 per unit. If recruitment rate >75% per cluster (50% reduction during training/transition period) then we would anticipate progression without significant changes. If 50-75% recruitment per cluster then we would consider adding additional sites. If recruitment rates <50% per cluster then progression to a full trial would be unlikely to occur. Analysis of recruitment rate and perceived barriers, will be undertaken at recruitment rates <100%. As an example of total numbers, with a recruitment rate of 75% in each cluster, based on average monthly admission numbers and including the transition period, a total of 1311 participants (average 31.2 patients per cluster/unit per month) would be recruited over 15 months (see, Section 2. FEASIBILITY SCHEDULE, Table 1: Project timeline).

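### Section 12.2 estimates the HAP utility decrement against age-sex matched controls, which discards non-HAP participants whose EQ-5D-5L, age and sex are collected anyway

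*Protocol*

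**What the plan says.** Protocol Section 12.2 sets out the comparison: "EQ-5D-5L questionnaires will be compared between a subset of patients who developed HAP, and from age-sex matched controls who did not develop HAP". Its purpose is given as "in order to estimate the utility decrement associated with HAP". No matching ratio is stated.

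The data needed for a wider comparison are already planned:

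- Sections 10.1.2 and 12.2 both plan EQ-5D-5L for all patients, with a proxy where needed and a follow-up at 90 days.
- Section 10.1.1 plans two baseline EQ-5D-5L assessments for all recruits, one describing health before admission and one describing current health.
- Table 3 lists age and sex among the covariates recorded for all recruited participants at study entry.

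Three other statements bear on the number of cases:

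- Section 3 gives the only incidence: "Approximately 1.5% of all hospital in-patients develop HAP (6".
- Section 5.2 gives an example total at 75% recruitment: "a total of 1311 participants (average 31.2 patients per cluster/unit per month) would be recruited over 15 months".
- HAP mortality has two ceilings. The Study Rationale in Section 1 says "Up to 70% of patients with HAP may die", and Section 3 says "It is a leading cause of death in hospitalised patients, with a mortality of up to 29% (2".

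**The concern.** Precision in a HAP versus non-HAP comparison is limited mainly by the number of HAP cases, which the study cannot choose. It can choose how many non-cases to use. Matching is worthwhile when each control costs money to measure. Here the controls are measured in any case, so a matched set saves nothing and gives up precision.

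Matching on age and sex does control those two variables. Regression can do the same with all the data, and it can also use pre-admission EQ-5D-5L, which the matching in Section 12.2 does not. At stake is a wider interval than the collected data allow, around an estimate that may already rest on few cases.

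**Working it through.** **Reproducing the protocol's total.** The recruited numbers in Table 1 sum by site to 504 + 392 + 280 + 135 = 1311. Over 42 unit-months, 1311 / 42 = 31.2 per unit per month. Both agree with Section 5.2.

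**Illustrative case count.** 1311 × 0.015 = 19.7, so about 20 HAP cases and 1311 − 20 = 1291 participants without HAP. Applying the two mortality ceilings gives 19.7 × (1 − 0.29) = 14.0 and 19.7 × (1 − 0.70) = 5.9 survivors. Both mortalities are upper limits, so at 1.5% incidence the range is about 6 to 20 before non-response.

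**Precision.** Assumptions not in the protocol: EQ-5D SD 0.30; 70% of non-HAP participants with a usable questionnaire (0.7 × 1291 = 904); no covariate adjustment; no within-pair correlation. With n HAP cases in the analysis:

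- 1:1 matching: 1.96 × 0.30 × √(2/n)
- 1:4 matching: 1.96 × 0.30 × √(1.25/n)
- all controls: 1.96 × 0.30 × √(1/n + 1/904)

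| HAP cases n | 1:1 | 1:4 | All controls | Narrower than 1:1 | Narrower than 1:4 |
|---|---|---|---|---|---|
| 6 | 0.34 | 0.27 | 0.24 | 29% | 10% |
| 14 | 0.22 | 0.18 | 0.16 | 29% | 10% |
| 20 | 0.19 | 0.15 | 0.13 | 29% | 10% |

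**Sensitivity to incidence.** At an assumed 5%, there are 1311 × 0.05 = 66 cases, leaving 47 survivors (29% mortality) or 20 (70%), and 0.7 × 1245 = 872 controls. With 47 cases the half-width is 0.12 for 1:1, 0.10 for 1:4 and 0.09 for all controls, a gain of 27% and 8%. With 20 cases it is 0.19, 0.15 and 0.13.

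**Sensitivity to response.** The table assumes that all n HAP cases respond. If 70% of 14 do (9.8), the half-widths are 0.27, 0.21 and 0.19; the gains are again 29% and 10%.

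The percentage gain does not depend on the SD, which cancels, and hardly depends on the case count. Its upper limits, with unlimited controls, are 1 − √(1/2) = 29% against 1:1 and 1 − √(1/1.25) = 11% against 1:4.

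**The case against.** **The ratio and the formula.** The protocol states no matching ratio, and a statistical analysis plan that is not shown could set one. With several controls per case most of the gain is already had; against 1:4 only about 10% remains. The half-widths also ignore any precision gained from correlation within matched pairs. All of this stands, and it makes the gain modest. It does not remove the point, because Section 12.2 itself fixes the matched design.

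**Confounding.** Dropping the matching with nothing in its place would leave age and sex uncontrolled. This also stands, so the change is sound only with covariate adjustment.

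**Stronger readings that the protocol does not support:**

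- A reader might infer that the study expects only 6 to 14 HAP survivors with a 90-day questionnaire. The protocol makes no such projection. The 1.5% refers to all hospital in-patients, whereas the target population is described as high risk and no incidence is given for these wards. The 1311 is an example, and both mortalities are ceilings without a time point. The 6 and 14 are also counts before non-response.
- A reader might infer that only some of the HAP cases would be analysed, because Section 12.2 speaks of a subset. Table 3 uses the same word for the population of patients with HAP, and a later sentence in Section 12.2 restates the comparison without restriction. The word probably just means those who develop HAP.
- A reader might infer that the estimate is promised as an input to the future economic model. Section 12.2 presents the economic work as feasibility, rules out a full evaluation and says the findings will refine methods.
- A reader might infer that the two mortality figures distort a calculation. They are background statements and enter none.

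**Conclusion.** The point holds as one of efficiency. For a comparison that may have few cases, the protocol chooses a matched design although the full set of controls and the covariates to adjust for are already being collected. Using all participants would narrow the interval by about 29% relative to 1:1 matching and about 10% relative to 1:4. The absolute half-widths rest on an assumed SD of 0.30 and assumed response; the percentages barely do. They are calculated before adjustment and without within-pair correlation.

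Whether the decrement would be too imprecise to use cannot be settled from the protocol, because that depends on the HAP incidence in these wards. The mortality ceilings of 70% and 29% do disagree, with no setting or time frame to explain the difference, but this is an editorial matter.

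**What to change.** In Section 12.2, replace the matched-control comparison with one that includes every participant with HAP and every participant without HAP who has EQ-5D-5L data. Estimate the difference by regression adjusted for age, sex and pre-admission EQ-5D-5L, and report it with its 95% CI as exploratory.

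One detail should be settled in the same edit. Section 10.1.1 asks about health one week before admission, while Section 12.2 refers hip-fracture patients to the day before the fracture. The adjustment needs a single definition.

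Separately, reconcile the HAP mortality figures in Sections 1 and 3, or state the setting and time frame of each.

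The cost is a change of wording and slightly more modelling work. No additional data are needed.
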